Effects of 12-week Digital Treatment in Patients With Hand OA on Pain and Function

NCT05499559

May 25, 2021

Malmö, Sweden

Survey of the field

Musculoskeletal conditions are identified by the Global Burden of Disease Study as a leading cause of global morbidity (1). Estimates of the need for rehabilitation services show that at least one in every three people in the world needs rehabilitation at some point in their life course (2). As disability becomes an increasingly large component of disease burden and health expenditure, greater research and development investment is needed to identify new, more effective intervention strategies (1).

Osteoarthritis (OA) is one of the leading causes of disability worldwide and due to its rising prevalence, the identification of appropriate care and care delivery modalities is a priority for the health care systems (3, 4). Exercise and education constitute the first-line intervention for people with knee, hip and hand OA and have been shown to be effective regardless of symptoms and disease severity (5, 6, 7) International guidelines recommend that first-line interventions for the majority of musculoskeletal conditions should involve nonsurgical management with exercise and education guided by a physiotherapist (PT) and based on a personalised care approach (8, 9).

OA of the hand is probably the most common form of OA and almost 50% of women and 25% of men will be affected during the life course (10). Self-management strategies includes a wide range of strategies such as education for strengthening or stretching exercises, joint protection education for activity and pacing, use of proper body mechanics, and assistive devices to improve pain, reduce inflammation, lower additional risk of deformities, and enhance performance (7). Systematic reviews that compared joint protection strategies to usual care have shown similar effects at short-term and superior effects at mid- and long-term compared to usual care (11).

To implement the guidelines, the Better Management of Patients with OsteoArthritis (BOA), a face-to-face concept including education and an option to exercise, has been developed and is offered at primary care clinics in Sweden since 2008 for patients with hip- knee- and hand OA (12). BOA has previously been found to reduce pain and improve function and quality of life in patients with hip and knee OA (9). Unfortunately, there is a discrepancy between recommended treatment and what patients receive and around 30% of people with OA seeking care go through first line management (13).

Traditional face-to-face interventions present barriers, such as limited access and lack of flexibility, which may limit the patients' adherence with the interventions (14). Digital delivery of the management program may be one way of overcoming such barriers (15, 16). Telehealth, defined as the 'delivery of healthcare at a distance using information and communication technology' could be a solution to many access barriers and has been rapidly adopted by many healthcare professions and accelerating even more throughout the COVID-19 pandemic (17,18).

Literature investigating the use of telehealth for the management of musculoskeletal pain is growing. Systematic reviews have demonstrated that telehealth can provide improvements in pain, physical function and disability that are similar to that of usual face-to-face care for individuals with musculoskeletal conditions such as osteoarthritis for the knee and hip (19, 20). The use of telehealth also seems to increase exercise adherence for a variety of musculoskeletal conditions (21, 22). To our knowledge, digital self-management programs for OA of the hand have not yet been evaluated.

Joint Academy® (JA), a digitally delivered treatment program with exercise and patient education was developed to increase access to and facilitate implementation of guideline derived and evidence-based treatment for OA. The first JA program was introduced in 2016 for persons with hip- and knee OA and participants reported reduced pain and improved function during up to 48 weeks of treatment (23). A recent randomised controlled trial on patients with knee OA showed that the digital program was superior to usual care (24). Since late 2021, a digital program for OA of the hand is also available on the platform.

Project description

This is an observational registry-based study.

Purpose and goal

The overall aim of this project is to evaluate changes in health outcomes during participation in the digitally delivered treatment programme Joint Academy® (JA) containing exercise and education for patients with osteoarthritis (OA) of the hand.

Specific research questions are:

(1) What are the short-term changes in health outcomes of digitally delivered treatment for OA of the hand? Primary outcome is to examine pain and perceived hand function in participants following 3 months of digitally delivered first-line treatment for hand OA

Main exposures and outcomes

All participants answer patient- and disease relevant socio-demographic and outcome questionnaires at baseline and every third month during treatment. Additionally, participants report pain every week.

Pain will be assessed using the Numerical Rating Scale (NRS, discrete boxes 0–10) with the instruction: “Mark on this scale how much pain you had the last week in your hand”, followed by a 0–10 scale where 0 was defined as *No pain* and 10 was defined as *Maximum pain* (25).

To evaluate hand function, the Functional Index for Hand OsteoArthritis (FIHOA) will be distributed. The FIHOA is a 10-item questionnaire based on a semi-quantitative assessment scoring the disease on a 4-point scale. The FIHOA has been shown to be valid, sensitive, clinically relevant for the population and shown consistency and acceptable reliability (26). The literature also suggests it is associated with pain, muscle strength and health related quality of life in people with hand OA (27).

Among other outcomes to be reported are health-related quality of life assessed with the EuroQol – 5 dimension descriptive system (EQ-5D-5L), work situation, medication use (dichotomous reply, yes/no), changes in medications, willingness for surgery (dichotomous reply, yes/no), physical activity, exercise, fear of physical activity (yes/no) and motivation to start exercising using a Numerical Rating Scale (NRS, discrete boxes 0–10).

All outcomes will be self-assessed and self-entered using the digital program interface. Demographic and socioeconomic data and data on the participants’ overall health and characteristics (e. g age, gender, educational level BMI) will be collected at inclusion. The exposure and outcome measures are described in Table 1.

The digital program Joint Academy®

In an attempt to scale and improve implementation of evidence-based guideline-derived first-line treatment for a number of musculoskeletal conditions (education and exercise), the digital self-management and education program Joint Academy® (JA) was developed in Sweden. The first JA program was developed in 2014 for persons with hip- and knee OA (28). The program for hand OA is available for patients since late 2021. The program is part of the health-care system in Sweden.

Participants join the programme through recommendation by their local physiotherapist (PT), occupational therapist (OT) or orthopaedic surgeon, via online advertisements and campaigns placed on search engines and social networks, or through their insurance company. A majority of included participants had a clinical diagnosis of hand arthritis from a PT, OT or physician, and all had a physical visit with a healthcare provider regarding their hand OA prior to joining JA. The clinical diagnosis of OA was confirmed by a PT or OT via telephone, or if deemed necessary the patient was recommended to seek face-to-face care before inclusion in the programme.

The Joint Academy® (www.jointacademy.com) program for people with hand OA consists of video instructed and progressively adaptable daily exercises, patient education through text lessons, possibility for a social chat group with other patients and a continuous asynchronous chat function with a personal reg. physiotherapist who supervises the patient during the full participation period. The program also contains three telephone consultations with a physiotherapist that were compulsory, one at the start, one after six weeks and one after three months. The intervention procedure is similar to that for hip and knee OA, which is thoroughly described in previous studies (23, 28).

Statistical analysis

We will develop a specific statistical analysis plan for each specific sub-study that will be conducted to answer the aforementioned research questions.

To describe the sample, we will use means and standard deviations (SDs), frequencies and percentages. These will follow several general principles. We will aim for the inclusion of all available patients to limit potential selection bias. In the statistical modelling we will aim for

estimation of causal effects and statistical models will be chosen accordingly using direct acyclic graphs (DAGs) to enable proper confounding control. For confounding control, we will use regression models or inverse probability weighting. For analysis of panel data (i.e. longitudinal repeated measurements of the participants and/or data clustered by caregiver) we will use conditional or marginal models. For time-to-event data we will use the Cox regression model, or, if appropriate, a parametric version. For mediation analysis, we will use linear models or maximum likelihood structural equation models when appropriate. For categorical outcomes we will use other approaches such as logit and probit models. We will report the results from all analyses as relevant estimated effect size (such as risk differences, risk ratios or hazard ratios) with 95% confidence intervals and interpret these for clinical relevance, irrespectively of statistical significance.

Power calculation

Power analysis revealed that for the initial short-term follow-up, a sample size of 70 participants will be enough to identify a minimally clinical important change of 1.5 units in pain with a calculated mean pain of 5.2 (sd 2.2) at start, power of 80%, $p<0.05$.

For the other studies, we will not perform any power calculation. This is because the question of power can be considered secondary in such a setting where the sample size is driven by data availability and not decided a priori. Therefore, we will include all the available data from the start.

Ethical considerations

Storage and management of data

The data set will be stored in a database at Arthro Therapeutics head office in Malmö. The platform is designed to securely store, manage and analyse data in accordance with the European Union general data protection regulation (GDPR). The process of linkage, storage and management of data, the role of informed consent in register-based research and safeguarding the integrity of study participants follows the legal and ethical frameworks as described by Swedish law and ethical boards. This has been described by Ludvigsson et al (30).

Data sharing

All information regarding individual patients is subject to confidentiality in accordance with The Public Access to Information and Secrecy Act (SFS 2009:400) chapter 25 article 1. Therefore, no unauthorised person will have access to data.

Significance

Preliminary results

- Initial observational reports on the first digital JA programme for persons with hip or knee OA suggest that participation in JA for six weeks was associated with a clinically relevant decrease in pain and an increase in physical function, as well as a decreased fear of physical activity (23). These effects were maintained up to 48 weeks during participation in the treatment program (29).
- Costing analysis of the JA program for persons with hip or knee OA have shown that the digital model overall costs around 25% of the existing face-to-face model of care (31).
- A Randomised Controlled Trial on patients with knee OA has shown that the digital JA programme was superior to routine treatment in a United Kingdom context (24).

Clinical significance

In the management of OA, overall adherence to clinical guidelines is low and implementation of strategies and removal of existing barriers against the application of evidence-based guidelines could facilitate the transfer of scientific evidence into clinical practice and contribute to optimising the quality of healthcare. Telehealth such as the digital JA program is scalable and has the potential to improve reach and access to evidence-based first-line treatment for a large number of individuals with musculoskeletal conditions who have internet access. Previous results for patients with knee and hip OA also suggest that the digital platform could offer a cost-effective alternative to the existing models of care. Depending on the extent to which the

digital model substitutes for the existing model of care, significant health-care resources can be saved.

Access to personnel

More than 250 physiotherapists are involved in JA and treating patients on a regular basis. Arthro Therapeutics has over 100 employees working with the design, adherence strategies and implementation of the platform, including operational team, research team etcetera.

References

1. Global burden of 369 diseases and injuries in 204 countries and territories, 1990-2019: a systematic analysis for the Global Burden of Disease Study 2019. *Lancet.* 2020;396(10258):1204-22

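### With pain and hand function both labelled primary, does the plan need a relevance threshold and a sample size for FIHOA as well as for pain?

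*Combined protocol and SAP*

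**What the plan says.** All places are in the combined protocol and SAP.

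- **Purpose and goal:** "Primary outcome is to examine pain and perceived hand function in participants following 3 months of digitally delivered first-line treatment for hand OA". Neither measure is ranked above the other, and no rule combines them. The research question itself asks what the short-term changes are.
- **Main exposures and outcomes:** pain is a 0–10 NRS. Of the function score it says: "The FIHOA is a 10-item questionnaire based on a semi-quantitative assessment scoring the disease on a 4-point scale". No direction of scoring, SD or important change is given.
- **Statistical analysis:** effect sizes from all analyses are reported "with 95% confidence intervals and interpret these for clinical relevance, irrespectively of statistical significance". The same section says: "We will develop a specific statistical analysis plan for each specific sub-study", tied to the research questions listed above it.
- **Power calculation:** "a sample size of 70 participants will be enough to identify a minimally clinical important change of 1.5 units in pain", from "a calculated mean pain of 5.2 (sd 2.2) at start", with 80% power at p<0.05. No FIHOA input appears.

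**The concern.** Two measures carry the primary label and only one is quantified. The plan sets significance aside and asks for a reading of clinical relevance, so the size of change that counts as relevant appears to carry the whole interpretation. For pain a reader can borrow the 1.5 units from the power statement. For FIHOA there is nothing to borrow.

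Two things could be at stake. First, if the FIHOA threshold were picked after the data were seen, one function result could be called relevant, inconclusive or not relevant. Second, if the primary label were taken to imply significance tests on both measures, the 5% and 80% figures would describe pain alone and not the pair.

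**Working it through.** **1. Reproduce the plan's figure.** Inputs from Power calculation: change 1.5, SD 2.2, power 80%, alpha 0.05 (two-sided assumed).

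- Two independent groups, normal approximation: n per group = 2 × (1.960 + 0.842)² × 2.2² / 1.5² = 33.8, so 34 per group and 68 in total.
- The t-test version gives 34.75, so 35 per group and 70 in total, with power 80.3%.

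The 70 is therefore a pain figure from a two-group formula. The study follows one cohort. With 70 complete pairs and SD of change = 2.2 × √(2(1 − ρ)), where ρ is an assumed correlation between baseline and follow-up:

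| ρ (assumed) | SD of change | Power for 1.5 units |
|---|---|---|
| 0 | 3.11 | 97.8% |
| 0.5 | 2.20 | above 99.9% |

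For pain, 70 is generous.

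**2. What 70 gives for FIHOA.** No sample size can be derived, because the document gives neither an SD nor a target. In units of the SD of change:

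- 95% CI half-width = t(0.975, 69) / √70 = 1.995 / 8.367 = 0.238 SD.
- Mean change detectable with 80% power (paired, two-sided 0.05): 0.34 SD.
- Power at assumed standardised changes of 0.2, 0.3, 0.4 and 0.5: 38%, 70%, 91% and 98.5%.

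So the pain calculation does not establish power for FIHOA. It also does not show that 70 is too few.

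**3. Does the reading depend on the threshold?** Assume a FIHOA mean improvement of 2.0 and try thresholds of 0.5, 2 and 3.5 (all assumed).

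| SD of change (assumed) | Half-width | 95% CI | Reading at 0.5 / 2 / 3.5 |
|---|---|---|---|
| 5 | 1.19 | 0.81 to 3.19 | relevant / inconclusive / not relevant |
| 8 | 1.91 | 0.09 to 3.91 | inconclusive at all three |

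The three-way split needs a half-width below 1.5, that is an SD below 1.5 / 0.238 ≈ 6.3. It shows that different thresholds can give different readings, which is true of any outcome. The estimate and interval are the same in every column.

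**4. Is the total score undefined?** Ten items with four levels each, scored as consecutive integers and summed, span 10 × 3 = 30 points. Only the origin and the direction are left open.

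**5. Error rates, if significance were used.**

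- Declaring success on either outcome at 0.05: 1 − 0.95² = 9.75% if independent; 9.1% at correlation 0.5; 8.3% at 0.7.
- Requiring both, each with 80% power: 0.8² = 64% if independent; 69% at 0.5; 71% at 0.7.

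Both lines presuppose a success rule. The plan states none, and its reporting sentence sets significance aside.

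**The case for a change.** The strongest case for a change is this. Function is in the study title and shares the primary label. Relevance is the only criterion the plan names for reading a result, and the document supplies a figure for pain and none for function. The promised sub-study analysis plan is not said to contain a FIHOA threshold. Writing one down would take two or three sentences and would change neither the sample nor the data collection. It would also remove any chance of choosing the yardstick after the result.

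The factual part stands: no important change and no scoring direction for FIHOA appear in the text, and the 80% power is for pain alone. A threshold fixed in advance would be an improvement.

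The inference does not follow. The relevance sentence is a principle for all analyses across the sub-studies. It contains no cut-off, and the plan nowhere says that pain results will be judged against "a minimally clinical important change of 1.5 units in pain"; that number is only a power input. A missing sample size does not stop anyone reading a confidence interval for relevance. The power statement already names pain as its subject, so it claims nothing for FIHOA. The worry about a late choice of threshold is conditional: absence from this document does not show that the point was left open until the data were examined.

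**Conclusion.** No change to the plan is called for. This is missing detail of a kind that analysts fill sensibly, in a document that defers such detail to a sub-study plan. Followed as written, the plan gives the mean change in FIHOA with a 95% confidence interval of about ±0.24 SD of change at 70 complete pairs, and a reader can hold any relevance threshold against it. The 9.75% either-outcome error and the 64% joint power (independent case) do not apply to an estimation-based, descriptive question. Powering on one of two outcomes is not an error in itself.

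This rests on two assumptions: that both outcomes are reported as estimates of change with no confirmatory claim, as the reporting sentence implies, and that about 70 participants have both measurements. It would need another look if a later analysis plan declared success on the basis of significance for either outcome.

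### The sample size of 70 matches a two-group t-test (35 + 35), but the study follows one cohort before and after treatment, so the stated power and detectable change do not describe it

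*Combined protocol and SAP*

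**What the plan says.** On the 3-month analysis, the Power calculation section states: "a sample size of 70 participants will be enough to identify a minimally clinical important change of 1.5 units in pain". Its other inputs are a baseline pain score averaging 5.2 with an SD of 2.2, a power of 80% and a significance level of 0.05. It does not give the test, the sidedness, a number of groups, an SD of change, a correlation between baseline and follow-up, or an allowance for loss.

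On design, the Project description says: "This is an observational registry-based study". Under Purpose and goal the first research question reads: "Primary outcome is to examine pain and perceived hand function in participants following 3 months of digitally delivered first-line treatment for hand OA". Under Main exposures and outcomes, participants answer "outcome questionnaires at baseline and every third month during treatment". No comparator group is described.

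The Statistical analysis section anticipates "longitudinal repeated measurements of the participants and/or data clustered by caregiver". It also commits to reporting effect sizes with 95% confidence intervals and to "interpret these for clinical relevance, irrespectively of statistical significance".

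**The concern.** A before-and-after comparison in one cohort depends on the SD of each person's change. The plan supplies only the SD of pain at a single time, and its sample size equals the total for two separate groups of 35. If that is where 70 comes from, the three linked figures (70 participants, 80% power, 1.5 units) describe a study that is not being done.

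This is the only planning figure for the primary question. As it stands, a reader cannot tell what change the study can detect or how precise the estimate will be. Precision matters most here, because the plan intends to judge intervals for clinical relevance rather than rely on significance.

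**Working it through.** **Inputs from the Power calculation section:** change δ = 1.5, SD at start = 2.2, α = 0.05, power 80%, n = 70. Two-sided testing is assumed because sidedness is not stated. The correlation r between baseline and 3-month pain is also an assumption and is shown as a range. All results use the noncentral t distribution.

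**1. Reproducing the plan's figure.** For a two-sample t-test, d = 1.5/2.2 = 0.682. For 80% power this needs 34.75 per group, rounded up to 35, so 70 in total. Power is 80.3% with 35 per group and 79.1% with 34. A one-sided version needs 28 per group (56 in total) and does not match.

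**2. The calculation for the design described.** For a paired t-test with SD 2.2 at both times, SD of change = 2.2 × √(2(1 − r)). The half-width at n = 70 is 1.995 × SD of change / √70.

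| r (assumed) | SD of change | n for 80% power | Power for 1.5 at n = 70 | Change detectable with 80% power at n = 70 | 95% CI half-width at n = 70 |
|---|---|---|---|---|---|
| 0 | 3.11 | 36 | 97.8% | 1.06 | 0.74 |
| 0.3 | 2.60 | 26 | 99.7% | 0.88 | 0.62 |
| 0.5 | 2.20 | 19 | >99.9% | 0.75 | 0.52 |
| 0.7 | 1.70 | 13 | >99.9% | 0.58 | 0.41 |

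The row for r = 0.5 also covers the reading in which 2.2 is itself the SD of change.

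**3. Could a paired test need 70?** Exactly 80% power for 1.5 with 70 pairs requires an SD of change of 4.42. With SD 2.2 at both times, r = 1 − 4.42²/(2 × 2.2²) = −1.02, which is impossible. After rounding up, the limiting case r = −1 also gives 70 (69.5), but it means perfectly inverse pain scores.

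**4. Could a different SD at 3 months explain it?** Let s be the 3-month SD. Then SD of change² = 2.2² + s² − 2 × r × 2.2 × s. Setting the left side to 4.42² gives s = 3.83 at r = 0, 4.55 at r = 0.3 and 5.08 at r = 0.5. On a 0–10 scale with mean 5.2 − 1.5 = 3.7, the largest possible SD is √(3.7 × 6.3) = 4.83. So r = 0.5 is ruled out, and the other two values are possible but implausible. With s between 1.8 and 2.6, the n needed is 31 to 43 at r = 0 and 17 to 23 at r = 0.5.

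**5. Could loss or clustering explain it?** No allowance is stated.
- At r = 0, 70 would imply 1 − 36/70 = 49% loss or a design effect of 70/36 = 1.9.
- At r = 0.5, it would imply 1 − 19/70 = 73% loss or a design effect of 70/19 = 3.7.

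Power for 1.5 units when fewer pairs are available:

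| Effective pairs | r = 0 | r = 0.5 |
|---|---|---|
| 49 (30% loss) | 91% | 99.7% |
| 42 (40% loss) | 86% | 99.1% |
| 35 (design effect 2) | 79% | 97.5% |

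**The case against.** The strongest reply is that the plan says only that 70 is enough, and for complete pairs at any non-negative correlation that is true with a margin. No test is named, so the two-group origin is an inference, and no sum is wrong on its own terms. Loss and clustering could also act together: 30% loss with a design effect of 1.4 leaves 49/1.4 = 35 effective pairs, and at r = 0 power for 1.5 units is then 79%, close to the stated 80%. The plan aims to include all available patients and promises a separate analysis plan for each sub-study, so the practical effect is small.

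Much of this stands. The origin is inferred, the error is conservative, and the impossibility in step 3 applies only to complete, independent pairs with equal SDs. It does not remove the point. The mismatch with a paired analysis holds wherever 70 came from, and no allowance for loss or clustering is stated. The combined route needs zero correlation between two pain scores from the same person, together with loss and clustering values that the plan does not give. The remark that sample size is driven by data availability is made about the other studies, not this one. A later analysis plan would not correct a figure already stated here.

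**Conclusion.** The concern holds. The stated combination of 70 participants, 80% power and 1.5 units reproduces exactly as a two-independent-group calculation and does not fit the single-cohort comparison that the plan describes. For that comparison, 13 to 36 participants suffice for r from 0.7 to 0. Seventy complete pairs give at least 97.8% power for 1.5 units, and the half-width is about a quarter to a half of 1.5.

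These figures assume SD 2.2 at both times, two-sided testing, independent pairs and complete 3-month data; r is not in the documents. Loss or clustering would lower the power. This is a moderate correction that should be made. It does not bias any estimate or leave the study too small under these assumptions. Confidence is high in the arithmetic and in the design mismatch; the formula originally used remains an inference.

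**What to change.** Replace the power sentence with a paired calculation that states the two-sided test, the SD of change (or the assumed correlation, labelled as an assumption and shown over r = 0 to 0.7), the number of participants expected to have 3-month data, and the 95% CI half-width. If the sponsor has an SD of change from its own data, that should replace the assumed correlation. Possible wording:

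> With 70 participants with 3-month data and an assumed SD of change of 2.2 (r = 0.5), a two-sided paired t-test at 0.05 has 80% power for a mean within-person change of 0.75 units and more than 99% power for 1.5 units; the 95% CI half-width is about 0.5. Over r = 0 to 0.7 the detectable change is 1.06 to 0.58 and the half-width 0.74 to 0.41. These figures assume independent pairs. Loss to follow-up or clustering by caregiver would lower power, for example to about 91% for 1.5 units with 49 pairs at r = 0.

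The cost is rewording one paragraph. Enrolment and data collection do not change.
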